#### 5.7. Interim Analysis

Not applicable

### 6. STUDY POPULATION

#### 6.1. Subject Disposition

Subject disposition information will be summarized and will include number of subjects screened, number of subjects included in the ITT population, the number of subjects completing the treatment phase of the study, the number of subjects completing the study through follow-up and primary reason for discontinuation.

#### 6.2. **Protocol Deviations**

Protocol deviations will be summarized by deviation category (major, minor). Additionally, protocol deviations will be presented in a data listing.

#### 6.3. Eligibility

Participants not fulfilling the eligibility criteria will be presented in a data listing.

#### 6.4. Demographic and Baseline Characteristics

Demographic variables include age, sex, ethnicity, race, and Fitzpatrick skin type. Age will be reported on the CRF and will be based on age at time of signing informed consent.

Baseline characteristics include intertriginous Physician Global Assessment (iPGA),

Unless otherwise noted, baseline is defined as the last non-missing value recorded before the first dose of study drug. Unscheduled visits will be used in the determination of baseline values, when applicable.

### 6.5. Medical History

Medical history will be coded using the Medical Dictionary for Regulatory Activities (MedDRA, version 26.0). The summary will show the system organ class (SOC) and preferred terms (PT) ordered alphabetically by SOC and descending PT frequency. The corresponding data listing by participant will be ordered by start date, end date, then alphabetically by preferred term.

Psoriasis history in the intertriginous areas will be summarized by duration of disease (<5 years, 5-10 years, >10 years) and by intertriginous areas affected.

#### 6.6. **Prior and Concomitant Therapy**

Prior and concomitant medication verbatim terms will be mapped to Anatomical/Therapeutic/ Chemical (ATC) class and preferred names using the WHODrug global dictionary (Version B3 01MAR2023).

Prior (within the 30 days before screening, and with stop dates prior to first dose of study drug) and concomitant (ongoing or with stop dates on or after first dose of study drug) medications will be listed by subject. If the medication is ongoing or the stop year is missing, the medication will be considered as received for the entire duration of the study.

To distinguish prior vs concomitant medications, the following rules for stop dates will apply:

- If only year was recorded, and it is before Baseline, it is a prior medication; if year is same or after Baseline, it is assumed to be a concomitant medication.
- If day is missing, but month and year are before Baseline, it is a prior medication; if month and year are the same as Baseline, it is assumed to be a concomitant medication; if month and year are after Baseline, it is a concomitant medication.
- If start date is after Baseline, it is a concomitant medication regardless.

Prior and concomitant medications will be summarized separately by WHO ATC 2 and preferred name. Subjects may have more than 1 medication per ATC 2 and preferred name. At each level of subject summarization, a subject is counted once if he/she reported 1 or more medications at that level. Frequencies and percentages of prior and concomitant medications will be ordered alphabetically by ATC class and descending preferred name. The corresponding data listing by participant will be ordered by start date of administration, end date of administration, then alphabetically by preferred name.

## 7. EFFICACY ANALYSES

All efficacy analyses will be performed based in the ITT population.

## 7.1. Efficacy Endpoints

The primary efficacy endpoint is the percentage of participants who achieve an iPGA score of clear (0) or almost clear (1) with a  $\geq$  2-grade improvement from Baseline at Week 12.

The secondary efficacy endpoint is the time to achieve an iPGA score of clear (0) or almost clear (1) with  $a \ge 2$ -grade improvement.

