5.2 Exclusion Criteria

Participants are excluded from the study if any of the following criteria apply:

Medical Conditions

1. Diagnosis of a type of psoriasis other than plaque PSO

- 2. Any sign of infection of any of the psoriatic lesions
- 3. Concurrent significant dermatologic or inflammatory condition other than plaque PSO that, in the Investigator's opinion, would make it difficult to interpret data or assessments during the study
- 4. A history of or ongoing serious illness or medical, physical, or psychiatric condition(s) that, in the Investigator's opinion, may interfere with participation in the study and ability to understand and give informed consent.
- 5. History of sensitivity to the study product, or components thereof or a history of drug or other allergy that, in the opinion of the Investigator or Medical Monitor, contraindicates participation in the study.

Prior/Concomitant Therapy

- 6. Previous OR current use of VTAMA.
- 7. Use of any prohibited medication within the indicated period before the Baseline visit.

NOTE: Prohibited concomitant medications, therapy, etc., during the defined period are as listed in the bullets below. If a participant requires any of these medications throughout the study period, he/she may be excluded from or discontinued from the study.

- Minimum of 5 half-lives for biologic agents: e.g., 12 months for rituximab; 8 months for ustekinumab; 5 months for secukinumab, risankizumab or tildrakizumab; 12 weeks for golimumab or guselkumab; 10 weeks for ixekizumab or infliximab; 8 weeks for infliximab, adalimumab, alefacept, or brodalumab; and 4 weeks for etanercept
- Four weeks for systemic treatments: deucravacitinib, cyclosporin, interferon, methotrexate, apremilast, tofacitinib, mycophenolate, thioguanine, hydroxyurea, sirolimus, azathioprine, other systemic immunosuppressive or immunomodulating agents, fumaric acid derivatives, vitamin D3 and analogs (> 5000 IU / day), retinoids (e.g., acitretin, isotretinoin), psolarens, corticosteroids, or adrenocorticotropic hormone analogs
- Two weeks for immunizations with a live viral component; drugs known to possibly worsen PSO, such as beta-blockers (e.g., propranolol), lithium, iodides, angiotensin-converting enzyme inhibitors, and indomethacin, unless on a stable dose for > 12 weeks

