6.9 Prior and Concomitant Therapy

Any medication or vaccine, including over the counter or prescription medicines, recreational drugs, vitamins, and/or herbal supplements, as well as non-medicated emollients, that the participant is utilizing at the time of consent or receives during the study must be recorded along with:

- Reason for use
- Dates of administration including start and end dates
- Dosage information including dose and frequency

The medical monitor should be contacted if there are any questions regarding concomitant or prior therapy.

Concomitant medications for medical treatment of other conditions are allowed, under the condition that the dosage and administration of these treatments are not planned to change from the Baseline visit to the completion of the study or discontinuation, and that the medication is not a prohibited medication as described in Section 5.2.

In the event of skin infection, topical antibacterial agents can be applied to the infected area; however, study product must not be applied to the area until the skin infection is healed.

Participants may use non-medicated shampoos (must not contain corticosteroids, vitamin D analogs, salicylic acid, or coal tar). Non-medicated emollients may be used outside of the intertriginous areas; emollients should not be applied to intertriginous skin. The same emollient should be used throughout participation in the study.

7 Discontinuation of Study Intervention and Participant Discontinuation/Withdrawal

Discontinuation of specific sites or of the study as a whole are detailed in Appendix 1.

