7.1.1 Temporary Discontinuation

Some dermatological reactions have been observed following treatment with VTAMA (tapinarof) cream, 1% (see Section 2.3.1). After cessation of exposure, dermatological reactions generally subside spontaneously or with topical treatments.

In this study, treatment of plaque PSO in intertriginous regions with study product may be interrupted for dermatological reactions. If treatment is interrupted due to a safety issue, the Medical Monitor will be contacted, and the event documented in the eCRF.

See Section 10.3.5 for further information on the management of follicular events.

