7.2 Participant Discontinuation/Withdrawal from the Study

- A participant may withdraw from the study at any time at the participant's own request for any reason (or without providing any reason).
- A participant may be withdrawn at any time at the discretion of the Investigator for safety or compliance reasons.
- At the time of discontinuing from the study, if possible, an early discontinuation visit should be conducted, as shown in the SoA. See SoA for data to be collected at the time of study discontinuation and follow-up and for any further evaluations that need to be completed.
- The participant will be permanently discontinued from the study product and the study at that time.
- If the participant withdraws consent for disclosure of future information, the Sponsor may retain and continue to use any data collected before such a withdrawal of consent.
- If a participant withdraws from the study, the participant may request destruction of any samples taken and not tested, and the Investigator must document this in the site study records.

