### 5.2. Analysis Populations

The intent-to-treat (ITT) population will include all participants enrolled in the study.

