#### 5.6. Missing Data

Every effort will be made to collect complete data at all visits.

All efficacy data will be summarized based on observed cases (OC).

Imputation of Missing Efficacy Data

In addition to the efficacy analysis based on OC, the primary and exploratory efficacy endpoints will also be summarized utilizing the last observation carried forward (LOCF) method to impute missing data

Baseline will not be used when applying LOCF and LOCF will be

implemented through Week 12 (i.e., Week 13 not included in LOCF). LOCF summaries will be considered supportive.

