## 7.2. Efficacy Analyses

[figure not shown]
Categorical endpoints will be summarized by presenting counts and percentages of subjects in corresponding categories. Percentages for missing values are omitted and do not account for the percent calculation of other categories. 95% confidence intervals will be presented.

Continuous endpoints will be summarized by presenting the number of observations, means, standard deviations, medians, minimums, maximums, and 95% confidence intervals.

The Kaplan-Meier product limit method will be used to estimate the median time to achieving an iPGA score of 0 or 1 with a  $\geq$  2-grade improvement from Baseline,

Categorical endpoints include:

• Percentage of participants who achieve an iPGA score of clear (0) or almost clear (1) with a ≥ 2-grade improvement from Baseline

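### On the visible text, a participant who uses prohibited anti-psoriatic therapy and then has a qualifying Week 12 iPGA counts as a responder; a supportive non-responder analysis would be a cheap addition

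*SAP*

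**What the plan says.** **Endpoint and analysis.** SAP 7.1: "The primary efficacy endpoint is the percentage of participants who achieve an iPGA score of clear (0) or almost clear (1", together with at least a 2-grade improvement from Baseline at Week 12. There is one analysis population (SAP 5.2): "The intent-to-treat (ITT) population will include all participants enrolled in the study". SAP 5.6 sets the main data handling: "All efficacy data will be summarized based on observed cases (OC". SAP 7.2 adds: "Percentages for missing values are omitted and do not account for the percent calculation of other categories". SAP 5.6 also gives a supportive LOCF summary of the primary endpoint, which deals with missing data only.

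**Prohibited therapy.** Protocol 6.9 allows concomitant medication for other conditions on the condition "that the medication is not a prohibited medication as described in Section 5.2". The note under exclusion 7 in Protocol 5.2 gives a discretionary consequence for a continuing need: "If a participant requires any of these medications throughout the study period, he/she may be excluded from or discontinued from the study". Protocol 7.2 is discretionary as well: "A participant may be withdrawn at any time at the discretion of the Investigator for safety or compliance reasons".

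**What the SAP does with the information.** SAP 6.2 summarises deviations as major or minor and lists them. SAP 6.6 summarises and lists concomitant medications. Neither section is linked to response status in the visible text.

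**The concern.** The primary objective is the efficacy of this product in intertriginous psoriasis. The study has a single arm, so no control group would show a contribution from other treatment. If a participant takes an effective prohibited agent and reaches a qualifying score because of it, the stated rule credits that response to the study product. The error runs in one direction, because effective extra therapy can turn a non-responder into a responder but not the reverse.

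Some on-study use is conceivable. Protocol 7.1.1 says of skin reactions: "After cessation of exposure, dermatological reactions generally subside spontaneously or with topical treatments". Protocol 7.1.2 then lets study product be resumed. The class of topical is not stated, so this shows a possible route and says nothing about frequency.

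At stake is how the reported response rate is read. The Kaplan-Meier onset estimate is touched only for users whose first qualifying score comes after first use.

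**Working it through.** The plan has no figure to reproduce: the 30 participants rest on clinical considerations, with no assumed response rate, dropout rate or rate of prohibited therapy use. The check follows the visible rules and then sizes the effect under stated assumptions.

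**1. What the visible rules do with a user of prohibited anti-psoriatic therapy**

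| Situation | Status under the visible rules |
|---|---|
| Stays in, qualifying Week 12 iPGA | Responder (SAP 7.1, 5.6) |
| Withdrawn late, qualifying iPGA at an early termination visit from Day 72 within the Week 12 window | Mapped to Week 12 by SAP 5.3, so responder |
| No Week 12 iPGA | Leaves the observed-case percentage (SAP 7.2) |
| No Week 12 iPGA, last earlier score after use and qualifying | Can be carried to Week 12 as a response under LOCF (SAP 5.6) |

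**2. Size per wrongly credited responder**

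Inflation in percentage points = 100 × k / n, where k is the number wrongly credited and n the number observed. Planned enrolment is about 30; 27 and 24 observed are assumptions.

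| n | k = 1 | k = 2 | k = 3 |
|---|---|---|---|
| 30 | 3.3 | 6.7 | 10.0 |
| 27 | 3.7 | 7.4 | 11.1 |
| 24 | 4.2 | 8.3 | 12.5 |

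**3. Comparison with the precision of the estimate**

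The visible text does not name the interval method, so exact (Clopper-Pearson) 95% limits are used. The base rate of two thirds is an assumption.

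- n = 30: 20/30 = 66.7% (47.2 to 82.7), half-width 17.8. With one user reclassified, 19/30 = 63.3% (43.9 to 80.1); with two, 18/30 = 60.0% (40.6 to 77.3).
- n = 27: 18/27 = 66.7% (46.0 to 83.5), half-width 18.7. With one, 17/27 = 63.0% (42.4 to 80.6); with two, 16/27 = 59.3% (38.8 to 77.6).
- n = 24: 16/24 = 66.7% (44.7 to 84.4), half-width 19.8. With one, 15/24 = 62.5% (40.6 to 81.2).

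One to three users shift the rate by less than the half-width in each case.

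**4. How likely is any user?**

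P(at least one among 30) = 1 − (1 − p)^30, for an assumed usage rate p per participant:

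- p = 0: 0%
- p = 1%: 26.0%
- p = 2%: 45.5%
- p = 5%: 78.5%

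This is the chance of any user, not of a wrongly credited responder. If half of users were wrongly credited (assumption), p is halved and the last three chances become 14.0%, 26.0% and 53.2%. If a fifth were, they become 5.8%, 11.3% and 26.0%.

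**The case against.** **Redaction.** The places that would hold such a rule are partly hidden. The LOCF sentence in SAP 5.6 breaks off, the Kaplan-Meier sentence in SAP 7.2 stops at a comma, and SAP 7.3 has no visible title or text. A reader might infer that the plan has no rule at all. The documents do not support that; the point holds for the visible text only.

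**No error in the main analysis.** Counting observed Week 12 status regardless of other therapy is a recognised approach, and the study is descriptive, with no test or success threshold. This stands. A reader might infer that the primary analysis is wrong or should be replaced; neither follows.

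**Listings.** With about 30 participants, efficacy data, deviations and medications are all listed, so any user can be found by hand. This stands in part: the listings identify users but do not give a response rate without the credit, and a choice made after seeing open-label data is weaker than one fixed beforehand.

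**Likelihood.** It is tempting to read Protocol 7.1.1 as allowing prohibited topicals for skin reactions, or to read 26.0 to 78.5% as the chance of bias. The first is not supported, because no class is named and Protocol 6.9 still applies. The second confuses any use with wrongly credited response. Even treating use as a protocol deviation is an inference from Protocol 6.9; Section 8.1.4 applies that label expressly to missed doses.

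**Lower bound.** Failing every user also fails those who would have responded anyway. This stands, and the supportive figure must be labelled accordingly.

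**Conclusion.** The point holds on the visible text as a cheap improvement. The stated rules count a prohibited-therapy user with a qualifying Week 12 iPGA as a responder, and LOCF can carry a qualifying post-use score to Week 12. Without a comparator arm the effect on the response rate can only be upward: 3.3 points per wrongly credited responder at n = 30 and 4.2 at n = 24. It is zero if there are no such users or if all of them would have responded anyway.

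The observed n below 30, the base rate, the usage rates and the number of users are assumptions. The conclusion that a small number of users moves the rate by less than the interval half-width rests on one to three users at a response rate of about two thirds. No test or decision rule changes.

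**What to change.** Keep the as-observed rate as the main figure. Before database lock, add one supportive analysis of the primary endpoint to SAP 7.2, in observed-case and LOCF form:

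- **Rule.** A participant who used a prohibited anti-psoriatic therapy after first dose and before the Week 12 iPGA counts as a non-responder. For LOCF, where the Week 12 score is missing, state the cut-off explicitly; the date of the score carried forward would serve.
- **Agents.** Take them from Protocol 5.2 and fix them as a list of preferred names before lock. Drugs listed only because they may worsen psoriasis, and the topical antibacterials permitted by Protocol 6.9, do not count.
- **Reason for use.** Use counts when the recorded reason is psoriasis or a skin reaction, for systemic as well as topical agents. A course taken for an unrelated condition then does not count.
- **Denominator.** Use the same one as the as-observed rate, so that missing data and therapy effect are not mixed. Show separately the number of users and how many of them have no Week 12 iPGA.
- **Label.** Describe the result as a conservative lower bound, because some users would have responded anyway.
- **Kaplan-Meier, if a matching run is done.** A response before first use stays an event. Other users stay in the risk set past the last observed event time. Censoring them at Day 85 would not do this, because the Week 12 window in SAP 5.3 runs to at least Day 87, so they would leave before any event recorded from Day 86.

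The cost is one SAP paragraph, one supportive row for each data handling and, optionally, one Kaplan-Meier run. Protocol 6.9 already requires reason for use and dates to be recorded. Application site and UV therapy are not among the items it lists, so the rule rests on reason for use and covers medications; state this as a limit. The downside is a little more work and a possibly slightly lower supportive rate. This is an analysis rule only and changes no one's treatment.

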## 7.2. Efficacy Analyses

[figure not shown]
Categorical endpoints will be summarized by presenting counts and percentages of subjects in corresponding categories. Percentages for missing values are omitted and do not account for the percent calculation of other categories. 95% confidence intervals will be presented.

Continuous endpoints will be summarized by presenting the number of observations, means, standard deviations, medians, minimums, maximums, and 95% confidence intervals.

The Kaplan-Meier product limit method will be used to estimate the median time to achieving an iPGA score of 0 or 1 with a  $\geq$  2-grade improvement from Baseline,

Categorical endpoints include:

• Percentage of participants who achieve an iPGA score of clear (0) or almost clear (1) with a ≥ 2-grade improvement from Baseline

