To assess onset of effect of VTAMA (tapinarof) cream, 1% in adults with intertriginous PSO	 Time to achieve an iPGA score of 0 or 1 with a ≥ 2-grade improvement from Baseline

Overall Design Synopsis:

Brief Summary:

The purpose of this open-label study is to evaluate the efficacy and safety of VTAMA (tapinarof) cream, 1% in adults with intertriginous PSO. Efficacy of the treatment of plaque PSO in intertriginous areas will be assessed with a PGA evaluation only of intertriginous areas (iPGA).

Participants will be allowed

to treat plaque PSO in other body areas according to instructions provided in USPI, but no assessments of efficacy will be performed outside of intertriginous

VTAMA will be dispensed and will be administered at home between clinic visits as instructed by site personnel. Application instructions will be reviewed at all clinic visits except during the final treatment/end-of-study visits. Participants will be instructed to apply cream QD to all affected areas, including intertriginous areas, and any other locations on the body. Existing lesions will be treated as well as newly appearing lesions and lesions/areas that improved or cleared during the study. Participants will apply sufficient cream to cover completely each lesion with a thin layer and will record the time of application in a daily diary provided by the study site. Participants will be instructed to maintain the approximate dosing time chosen at the beginning of the study for their full study participation.

Number of Participants:

Approximately 30 participants will be enrolled.

Note: Enrolled means participants agreement to participate in a clinical study following completion of the informed consent process and screening. Potential participants who are screened for the purpose of determining eligibility for the study, but do not participate in the study, are not considered enrolled, unless otherwise specified by the protocol. A participant will be considered enrolled if the informed consent is not withdrawn prior to participating in any study activity after screening.

Study Arms and Duration:

VTAMA (tapinarof) cream, 1% is a white to off-white cream containing 1% weight/weight (10 mg/g) tapinarof, supplied in 60-gram tubes. VTAMA is to be administered by the participant QD via topical application of a thin layer to affected areas in accordance with instructions in USPI.

Dosing may be interrupted if deemed necessary by the Investigator for management of adverse events.

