8.2.1.1 Physician Global Assessment of Intertriginous Areas

The PGA is a clinical tool for assessing the current state/severity of a participant's PSO at a given time point. It is a static 5-point morphological assessment of overall disease severity, as determined by the Investigator, using the clinical characteristics of erythema, scaling, and plaque thickness/elevation as guidelines; higher PGA scores represent more severe disease (see Appendix 5).

In this study, the PGA should be used only to assess plaque PSO in intertriginous areas (iPGA).

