## 2.2. Secondary Objectives

The secondary objective of the study is to assess onset of effect of VTAMA (tapinarof) cream, 1% in adults with intertriginous PSO.

[figure not shown]

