# 5. STATISTICAL CONSIDERATIONS

### 5.1. General Considerations

will perform the statistical analysis of the data. SAS version 9.4 or higher will be used to generate all statistical outputs (tables, listings, figures [TLFs], and datasets). The International Council for Harmonisation (ICH) numbering convention will be used for all TLFs. Continuous endpoints will be summarized by presenting the number of observations, means, standard deviations, medians, minimums, and maximums. The 95% confidence intervals will be reported as appropriate.

Time to event analyses will use the Kaplan-Meier product limit method (if estimable) based on observed cases.

Categorical endpoints will be summarized by presenting counts and percentages of subjects in corresponding categories. All possible categories as defined in the case report form (CRF) will be populated, even if they have zero counts. With the exception of ethnicity and race in the demographic table, percentages for missing values are omitted and do not account for the percent calculation of other categories. In certain tables (e.g., TEAEs), the total number of subjects is used as denominator. Footnotes will specify the percent basis in those cases.

Individual subject data obtained from the eCRFs and any derived data will be presented by subject in data listings.

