#### 5.3. Analysis Windowing

Study days are measured from date of first dose of study medication. Study days corresponding to measurements are calculated as:

- Assessment date date of first dose + 1 if assessment date is on or after the date of first exposure of treatment.
- Assessment date date of first dose if assessment date is before the date of first exposure of treatment.

All efficacy and safety endpoints will be analyzed according to the nominal visits (i.e. actual visit) except for assessments collected on early termination and unscheduled visits. Early termination and unscheduled visits will be re-numbered to an analysis visit based on their windowed visits defined by actual study day. If more than one visit occurs within a single visit window, then the analysis will take the one closest to the target day. If the 2 visits are equidistant from the target day, the visit with later date and time will be used.

Analysis Visit	Target Day	Analysis Visit Window
Baseline (1)	1	1
Week 1	8	Post first dose to Day 12
Week 2	15	Day 13 – Day 22
Week 4	29	Day 23 – Day 36
Week 6	43	Day 37 – Day 50
Week 8	57	Day 51 – Day 71
Week 12	85	Day 72 – Maximum (last day of treatment + 3 days, Day 87)
Week 13	92	> Maximum (last day of treatment + 3 days , Day 87)

The following analysis visit windows will apply to early termination and unscheduled visits:

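### Does a Kaplan-Meier median misstate onset of effect when iPGA response is seen only at visits 7 to 28 days apart?

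*SAP*

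**What the plan says.** SAP 2.2 states the aim: "The secondary objective of the study is to assess onset of effect of VTAMA (tapinarof) cream, 1% in adults with intertriginous PSO". SAP 7.1 makes this operational as the time to reach an iPGA of 0 or 1 with at least a two-grade improvement. SAP 7.2 gives the summary: "The Kaplan-Meier product limit method will be used to estimate the median time to achieving an iPGA score of 0 or 1". Protocol 9.3.3 names the same method, and SAP 5.1 adds: "Time to event analyses will use the Kaplan-Meier product limit method (if estimable) based on observed cases". The sentence just before that one in SAP 5.1 allows 95% confidence intervals where appropriate.

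On how response is observed, Protocol 8.2.1.1 says of the scale: "It is a static 5-point morphological assessment of overall disease severity, as determined by the Investigator". On timing, SAP 5.3 says: "All efficacy and safety endpoints will be analyzed according to the nominal visits (i.e. actual visit) except for assessments collected on early termination". The same exception covers ratings at unscheduled visits. Its window table lists target days 1, 8, 15, 29, 43, 57, 85 and 92.

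Protocol 9.1 and SAP 5.4 rule out inferential testing. About 30 participants are planned in one arm.

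Two things cannot be seen in the public text. The schedule of activities is not shown, and the Kaplan-Meier sentence in SAP 7.2 breaks off after a comma. An event date, a censoring rule or a label may stand in the missing words, so their absence is not counted against the plan.

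**The concern.** A static rating dates a response only at the visit where it is first recorded. True onset lies somewhere between the last visit without response and the first visit with it. A Kaplan-Meier analysis that uses the visit day as the event time takes the right end of that interval. A reported median of Day 43 would then mean only that the estimated median falls after Day 29 and by Day 43.

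Onset of effect is the sole secondary objective, and Protocol 4.2 stresses how much speed of onset matters to patients. A reader who takes the median at face value could think the cream slower than it is. Treating onset as interval-censored, reporting the median as a between-visit interval and adding cumulative response by visit looks like a cheap improvement on the same data.

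**Working it through.** The documents give no expected median, event count or power for this endpoint, so there is no figure of the plan's own to reproduce.

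**Inputs from the documents.** Target days from SAP 5.3; n = 30 from SAP 4.

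**Assumptions.** iPGA is rated at every listed visit. The first response visit is the event time. Response is sustained and nobody drops out. Study day is used as the time scale. Onset is Weibull with median m and shape k: F(t) = 1 − exp(−ln 2 × (t/m)^k). The Kaplan-Meier median is the first visit at which at least half have responded.

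**Step 1, the grid.** Differences of days 1, 8, 15, 29, 43, 57, 85, 92 are 7, 7, 14, 14, 14, 28 and 7 days.

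**Step 2, large samples.** The median becomes the first visit at or after the true median. Day 10 gives 15 (+5), Day 20 gives 29 (+9), Day 36 gives 43 (+7), Day 50 gives 57 (+7) and Day 65 gives 85 (+20). The delay runs from 0 to just under one gap. It is less than 7 days when the true median falls by Week 2 and can approach 28 days between Weeks 8 and 12.

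**Step 3, n = 30.** P(median ≤ visit v) = P(Binomial(30, F(v)) ≥ 15). Mean lag is the integral of (next visit − t) f(t) up to Day 85, divided by F(85). For k = 1.2:

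| True median | Typical estimate | Estimate later than truth | Mean lag per responder (days) |
|---|---|---|---|
| Day 20 | Day 29 | 86% | 6.7 |
| Day 36 | Day 43 | 78% | 7.9 |
| Day 50 | Day 57 | 69% | 8.3 |
| Day 65 | Day 85 | 66% (7% not estimable, included) | 8.5 |

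For true Day 36, the estimate is Day 29 in 22% of trials, Day 43 in 63%, Day 57 in 15% and Day 85 in 1%. The last three sum to 78% before rounding. Shapes 0.8 and 2.0 give the same typical medians and mean lags of 6.4 to 9.7 days.

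**Step 4, what the alternative adds.** With complete visits, the interval-censored (Turnbull) estimate equals the Kaplan-Meier estimate at each visit day. Its between-visit interval is the Kaplan-Meier median paired with the preceding visit. The chance that this interval contains the true median is the chance that the Kaplan-Meier median lands on the right visit:

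| Shape | Day 20 | Day 36 | Day 50 | Day 65 |
|---|---|---|---|---|
| 0.8 | 66% | 45% | 33% | 43% |
| 1.2 | 84% | 63% | 48% | 59% |
| 2.0 | 97% | 86% | 71% | 78% |

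**Step 5, the median with a confidence interval.** At true Day 36 and k = 1.2, F at Days 15, 29, 43 and 57 is 0.215, 0.414, 0.576 and 0.700, or about 6, 12, 17 and 21 of 30. A 95% order-statistic interval for a median at n = 30 uses the 10th and 21st responders: P(10 ≤ Binomial(30, 0.5) ≤ 20) = 95.7%. They fall at about Day 29 and Day 57. The output would read Day 43 (95% CI 29 to 57), which shows both the grid and the sampling error.

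**Step 6, missed visits.** Suppose each visit before Week 12 is missed independently with probability 0.10. The Kaplan-Meier response curve at visit j is then low by the sum over i ≤ j of p_i × 0.10^(j−i+1), where p_i is the onset probability in gap i. For true Day 20, k = 1.2, at Day 29: 0.10 × 0.273 + 0.01 × 0.182 + 0.001 × 0.206 = 0.029. Across the four scenarios the shortfall at Days 8 to 57 is about 0.5 to 2.9 percentage points. At shape 2.0 it reaches 4.7 points.

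**The case for a change.** The best case for a change is that the aim is worded as onset, the visible text does not label the median as first documented response, and a label with a cumulative table costs a few lines. The by-visit response percentages are not a full substitute. SAP 7.2 says: "Percentages for missing values are omitted and do not account for the percent calculation of other categories", so they leave out participants without a rating, and they count a lost response as non-response. In a descriptive study the reported number is the result, so its meaning matters.

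The interpretive part of this stands. The lag is real under the stated assumptions, and a report that called Day 43 the moment of onset would overstate what was seen. The rest does not lead to a different analysis. The endpoint in SAP 7.1 is the time to a score, and a score exists only when rated, so time to first documented response is what the plan estimates. The cumulative response asked for is what the planned Kaplan-Meier curve already estimates. The between-visit interval also has a cost: it looks like a measure of uncertainty but carries no sampling error, and at n = 30 it often excludes the true median.

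**Conclusion.** No change to the plan is needed. Kaplan-Meier on visit days is a valid and common summary of time to first documented response. The interval-censored alternative leaves the visit-day estimates unchanged when visits are complete and moves them by a few percentage points under 10% random missed visits. Replacing a median that may carry a 95% confidence interval with a range that, at shape 1.2, misses the true median in 16% to 52% of trials (up to 67% at shape 0.8) is at best a debatable trade.

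What remains is a matter of wording in the study report: the median describes first documented response, and true onset may be earlier, with a mean lag of about 6 to 10 days per responder across the scenarios examined. These figures assume n = 30, no dropout, sustained response, Weibull onset with shape 0.8 to 2.0, true medians of Day 20 to 65, and iPGA rated at each target day. Faster onset would shrink the lag. Informative dropout could offset or reverse it, and neither method cures that. No test, comparison or primary result depends on the point.
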